#### Study Protocol

# Effects of transcranial electrical stimulation combined with retrieval practice on semantic memory in patients with schizophrenia

### **1. Introduction**

Research on semantic memory in schizophrenia patients has revealed weaker activation in the prefrontal cortex, potentially linked to cognitive impairments [1,2]. Prior studies have suggested that continuous periodic tES intervention in the left dorsolateral prefrontal cortex (L-DLPFC) can enhance semantic recognition abilities [3]. Semantic memory organization in schizophrenia patients approaches that of healthy individuals after undergoing continuous tES stimulation of the left DLPFC for five days, ten times [4]. Thus, stimulating the excitability of the L-DLPFC through tES can effectively ameliorate semantic memory impairments in schizophrenia patients and is the preferred area for interventions in semantic memory treatment.

As an effective learning strategy, retrieval practice can assist patients in enhancing semantic elaboration and boosting memory performance [5]. Research utilizing near-infrared brain imaging technology to observe brain regions during retrieval practice has revealed that during challenging word retrieval tasks, activation levels in the inferior frontal gyrus, Frontal polar region, and dorsolateral prefrontal cortex area are significantly higher compared to conditions without retrieval, aligning closely with the regions activated by tES [6]. This suggests that there is consistency in brain activation between tES and retrieval practice, and combining the two may result in mutually reinforcing effects.

A study involving 119 healthy subjects investigated the combination of tES intervention with retrieval practice and found that the strong retrieval practice effect left no room for tES to improve memory performance[7]. The combination of single-session online tES with retrieval practice in healthy individuals and found that the memory performance of anodal stimulation was inferior to cathodal stimulation and sham stimulation [8]. We have already explored the role of continuous periodic tES combined with interim testing on spatial route learning in patients with schizophrenia in a previous study [9], and found that both the learning strategy and tES independently facilitated the ability of patients with schizophrenia to learn new information in spatial route learning, suggesting that the tES of L-DLPFC has a significant improvement effect. In contrast, targeted tES treatment may be more effective for memoryimpaired populations such as schizophrenia [10]. Therefore, further investigation is needed to determine the effectiveness of combining tES and retrieval practice for semantic memory intervention in schizophrenia patients. From a theoretical perspective, this combination may have a dual activation effect because (1) tES stimulation can enhance activation levels of the L-DLPFC, improving its cognitive function impairment; (2) retrieval practice can not only help patients initiate semantic memory strategies and promote semantic elaboration but also actively activate the brain regions stimulated by tES, thereby producing a synergistic effect.

Therefore, this study aims to investigate whether combining tDCS, tACS with retrieval practice facilitates the maintenance of semantic memory and improvement of semantic organization by comparing the use of retrieval practice strategies in patients receiving anodal L-DLPFC stimulation, sham stimulation.

#### 2. Methods

#### 2.1 Participants

60 schizophrenic patients plan to be recruited from the mental health center. All patients must sign an informed consent form.

Patients with schizophrenia are diagnosed and assessed by two chief psychiatrists. Neuropsychological background tests included the Montreal Cognitive Assessment (MoCA)[11] for general cognitive function and the Positive and Negative Syndrome Scale (PANSS)[12]. A parallel-group, single-blind study design was used to assign subjects to the two stimulus types using a stratified randomization method based on baseline Montreal Cognitive Assessment performance. The characteristics of the participants are presented in Table 1, showing no significant differences in participant characteristics between the two stimulation types groups.

Patients with schizophrenia were included based on the following criteria: (1) meeting the diagnostic criteria for schizophrenia according to the Diagnostic and Statistical Manual of Mental Disorders, Fifth Edition (DSM-5); (2) aged 18 years or older, regardless of gender, with an educational level of elementary school or above; (3) all patients received stable-level antipsychotic medication treatment, were in a stable phase of disease treatment, able to understand the testing requirements, and cooperated to complete all research tasks; (4) no history of neurological disorders or other serious physical illnesses, and no history of intellectual disability; (5) no color blindness, color weakness, or other color vision impairments, with normal vision or corrected vision.

Exclusion criteria were as follows: (1) clear cognitive impairment caused by somatic or cerebral organic lesions, such as cerebrovascular diseases, traumatic brain injury, etc; (2) individuals with mental disorders caused by substance dependence or abuse, or the use of psychoactive substances; (3) history of brain injury or other central nervous system-related organic diseases; (4) individuals at significant risk of suicide or harming others; (5) participation in similar experiments in the past 30 days prior to baseline.

#### 2.2 Design

A mixed experimental design of 3 (Stimulation type: tES stimulation, tACS stimulation, sham stimulation)  $\times$  2 (Learning strategy: retrieval practice, restudy)  $\times$  2 (Retention interval: Immediate recall, Delayed recall) was employed. Stimulation type was a between-subjects variable, while learning strategy and testing time were within-subject variables. The dependent variables were the correct recall rate and Adjusted Ratio of Clustering (ARC) scores in the testing phase.

#### 2.3 Devices and Materials

#### 2.3.1 Devices

The direct current stimulation device powered by batteries used in this study was the Starstim system from NE (Neuroelectrics) company in Spain. All groups utilized the same electrode montage, and the electrode placement followed the international 10-20 system for electroencephalography. The tES intervention employed 8 cm^2 circular sponge electrodes. The anode was placed over F3 (i.e., L-DLPFC) and the cathode over FP2 (i.e., right supraorbital area).

#### 2.3.2 Materials

Thirty-four words from eight common semantic categories were selected as the learning materials. Among them, five words were chosen from each of the six categories (fruits, clothing, musical instruments, sports, stationery, media) as experimental items, while two words were selected from each of the remaining two categories (daily necessities, body organs) as filler items. These filler items were presented at the beginning and end of the learning list to control for primacy and recency effects, respectively.

The selection of experimental categories followed the following rules:(1)To control for the mutual influence between categories, relatively unrelated categories were chosen (the main control was the degree of association between categories and their knowledge domains, such as choosing between fruits and vegetables); (2)Two-character words with clear semantics were selected as sample words. The selection of sample words followed these rules: 1) Each sample word was a two-character word with clear semantics; 2) Each sample word had a different pronunciation [13].

Prior to the formal experiment, 20 schizophrenia patients were randomly selected as participants to assess the semantic familiarity and relevance of 30 pairs of category sample word pairs. Evaluation was conducted on a Likert five-point scale (1 indicating complete unfamiliarity or no relation, and 5 indicating complete familiarity or very close relation). The results indicated that there were no significant differences between the familiarity (M = 4.42, SD = 0.76) and relevance (M = 4.75, SD = 0.47) of the retrieval practice list (fruits, clothing, instruments) and the familiarity (M = 4.61, SD = 0.59) and relevance (M = 4.65, SD = 0.45)

of the restudy list (sports, stationery, media), *t*(19) = -1.765, *p* = .094, 95% CI [-0.41, 0.03], *t*(19) = 1.344, *p* = .195, 95% CI [-0.05, 0.25].

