#### (2) Learning phase

The experimental procedure followed the classic retrieval practice paradigm, which included a learning phase and a final test phase.

During the experiment, participants were informed that they would learn two lists of

words. Subsequently, they might either learn the words again or complete a list recall test, and will be given a final test shortly thereafter. The learning of the retrieval practice list and the restudy list was conducted in a randomly balanced manner. Each word was presented for 5 seconds, with a 500-millisecond interval between words. To avoid providing secondary retrieval cues between examples, all words were shuffled pseudo-randomly within categories. Each list contained 17 words, consisting of 5 examples from each of the 3 experimental categories (15 experimental examples, 2 filler examples). The first and last words presented in each list were filler words, thus controlling for the primacy and recency effects on memory.

For the retrieval practice list, participants underwent two learning sessions and two retrieval sessions (S-T-S-T). During retrieval, participants were instructed to write down all the words they had just remembered within 5 minutes. For the restudy list, participants underwent four study sessions (S-S-S). Between each learning cycle, participants completed a 3-minute simple arithmetic task (dispersed attention task).

(3) Testing phase

Immediate Test: Participants were instructed to recall as many words as possible from the learned lists within 10 minutes after completing all learning tasks.

Delayed Test: Participants were informed to recall as many words as possible from the

learned lists within 10 minutes 24 hours later.

Figure 1. Experiment procedure.

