#### 2.5 Date scoring & analysis

The experimental results were processed using SPSS 26.0. The correct recall rate of word lists was calculated for each subject by the experimental assistant. Then, Free recall organization was measured by the Adjusted Ratio of Clustering (ARC) scores [14,15]. ARC scores range from 1 to 1. A 0 score indicates a level of clustering similar to what would be expected by chance, and a score of 1 implies perfect clustering. Negative values of ARC scores mean atypical and uninterpretable recall patterns[16]. For that reason, negative scores were excluded from analyses.

A mixed-design analysis of variance (ANOVA) was conducted to compare the correct recall rates and ARC clustering scores between the two learning strategies under two stimulation conditions. All statistical tests were performed at a significance level of 0.05, and post-hoc comparisons were adjusted using Bonferroni correction. Effect sizes were reported using partial eta-squared ( $\eta_p^2$ ; ANOVAs).

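### Each word set is tied to one learning strategy and no rotation is stated, so the strategy effect on recall and clustering cannot be separated from list content

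*Protocol*

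**What the plan says.** Section 2.2 makes strategy a factor that every patient meets at both levels: "Stimulation type was a between-subjects variable, while learning strategy and testing time were within-subject variables". Section 2.3.2 links the word sets to the strategies by name. One set of ratings is that "of the retrieval practice list (fruits, clothing, instruments"), the other that "of the restudy list (sports, stationery, media"). In 20 patients the two lists did not differ significantly in rated familiarity or relevance.

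Section 2.4 (2) contains the only sentence on balancing: "The learning of the retrieval practice list and the restudy list was conducted in a randomly balanced manner". It does not say what is balanced. The same section gives the lists an equal structure: "Each list contained 17 words, consisting of 5 examples from each of the 3 experimental categories".

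Section 2.5 plans a mixed ANOVA to "compare the correct recall rates and ARC clustering scores between the two learning strategies under two stimulation conditions" and names no list term. Section 2.1 assigns stimulation by a "stratified randomization method based on baseline Montreal Cognitive Assessment performance"; word set plays no part in it.

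**The concern.** A within-patient comparison of two strategies needs different words for each strategy, because a patient cannot learn the same words afresh twice. The usual safeguard is to let each word set serve under each strategy in half the patients. Nothing in the protocol says this is done, and the labels in Section 2.3.2 suggest it is not.

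If the sets are fixed, strategy and word set are the same variable. A list that is easier to recall, or easier to cluster by category, produces a strategy effect that is really a materials effect. More patients only make the wrong quantity more precise, and no later model can separate two variables that never differ. The strategy by retention interval term is exposed in the same way if the two sets are forgotten at different rates. The strategy comparison matters here: it is tested in Section 2.5, and the Introduction asks whether the combination "facilitates the maintenance of semantic memory and improvement of semantic organization by comparing the use of retrieval practice strategies".

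**Working it through.** **1. The pilot figures (Section 2.3.2), reproduced.** Paired t, 19 df, critical value 2.093; SE = |difference| / |t|.

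- Familiarity: 4.42 − 4.61 = −0.19; SE = 0.19 / 1.765 = 0.108; CI = −0.19 ± 2.093 × 0.108 = −0.415 to 0.035 (stated −0.41 to 0.03); p = 0.094, as stated.
- Relevance: 4.75 − 4.65 = 0.10; SE = 0.10 / 1.344 = 0.074; CI = −0.056 to 0.256 (stated −0.05 to 0.25); p = 0.195, as stated.

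Both agree within rounding. The standardised paired differences, t / √20, are −0.39 and 0.30, in opposite directions. With 20 raters the power to detect a standardised difference of 0.3 is about 25%, and of 0.4 about 40%. Non-significance therefore does not show that the lists are equivalent. The ratings also measured neither recall nor clustering, which are the outcomes.

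**2. What the strategy contrast estimates.** For each patient let D = recall under retrieval minus recall under restudy. Let S be the strategy effect and L the recall advantage of the first word set.

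- Fixed lists: the mean of D is S + L for everyone. Only the sum can be estimated.
- Rotated lists: the mean of D is S + L in one half and S − L in the other. The average is S, and half the difference between the halves is L.

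**3. Illustrative size.** From the protocol: 60 patients, three arms (Section 2.2), 15 scored words per list, alpha 0.05. Assumed: no true strategy effect (S = 0); SD of D between 10 and 25 points; list differences of half a word and one word. One word is 100 / 15 = 6.67 points.

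The strategy test is F(1, 57), with noncentrality 60 × (L / SD)². For example, half a word at SD 10 gives 60 × (3.33 / 10)² = 6.67. Chance of a false significant strategy effect with fixed lists:

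| SD of D (points) | L = half a word (3.33) | L = one word (6.67) |
|---|---|---|
| 10 | 72% | over 99% |
| 15 | 40% | 92% |
| 20 | 25% | 72% |
| 25 | 17% | 53% |

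**4. Effect of rotation.** Simulation of 4,000 trials, SD 15, 20 patients per arm (equal allocation assumed, as no ratio is given), L = 6.67, S = 0:

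| Design and model | Strategy falsely significant | Mean bias (points) | Stimulation × strategy falsely significant |
|---|---|---|---|
| Fixed lists | 92% | +6.67 | 5.0% |
| Rotated, list term in model | 4.8% | 0.01 | 5.0% |
| Rotated, no list term | 3.1% | – | – |

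Without the term, the list difference stays in the residual and the test becomes conservative; hence the term.

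**5. The interaction.** A list difference common to all arms cancels in stimulation × strategy, as the 5.0% shows. If instead one arm alone changed performance on one word set by 6.67 points, that test would be falsely significant in 27% of trials with fixed lists and 4% with rotation.

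**The case against.** The strongest reply is that the balancing sentence in Section 2.4 (2) may have been meant to cover rotation. Figure 1, which is said to show the procedure, is not in the text available for this review and might show it. This is possible. But the sentence balances lists that already carry a strategy name, and a set that rotated could not properly be called the retrieval practice list. Even on the favourable reading, the two sections need reconciling.

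Second, the main question is whether stimulation adds to retrieval practice. That rests on the stimulation effect and on stimulation by strategy, and a constant list difference biases neither. This stands and limits the scope. The strategy effect is nevertheless a tested result of the planned ANOVA.

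Third, the error rates rest on assumed SDs and assumed list differences, and they suppose no true strategy effect. If an effect exists, as the protocol expects, the harm is a mis-sized estimate rather than a false positive. This also stands. The lists were built with common selection rules and equal structure, and the rating differences do not favour one list consistently. These steps make a large difference less likely but do not exclude one.

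Finally, the missing list term in Section 2.5 counts for little by itself, because an analysis plan could supply it. The assignment of words to strategies is different: it is fixed when the patient is tested, and no analysis plan can repair it.

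**Conclusion.** The concern holds. As the protocol is written, learning strategy and word set coincide for every patient, and the strategy effect on recall and ARC cannot be separated from list content. The same applies to strategy by retention interval.

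The bias equals the list difference, whose size and direction the documents do not give. Under the stated assumptions, half a word raises the false-positive rate of the strategy test to between 17% and 72%, and one word to between 53% and over 99%. The stimulation main effect is not biased. Stimulation by strategy is at risk only if stimulation acts differently on the two word sets.

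Confidence is moderate, because the reading rests on an ambiguous sentence and on labels that point towards fixed sets. This should be fixed before enrolment.

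**What to change.** Before the first patient:

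- In Section 2.3.2, rename the lists set A and set B, without a strategy label.
- In Section 2.4 (2), state that half the patients in each stimulation arm retrieve A and restudy B, and half the reverse, with learning order also balanced.
- In Section 2.1, assign the list version within the MoCA-stratified randomisation.
- In Section 2.5, add list assignment as a between-subject factor. Its interaction with strategy carries the list difference.

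If rotation was already intended, it is enough to correct the labels and the balancing sentence so that they say so, and to name the model term.

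The cost is a second version of the list scripts and one more balancing factor. With three equal arms, 60 / 3 / 2 = 10 patients per list version per arm; balancing order as well gives 5 per cell. An additive list term lowers the error df for the strategy test from 57 to 56. Crossing list with arm in full lowers it to 60 − 6 = 54. Either loss is small. No extra patients or visits are needed, and the protocol's status section says that recruitment has not begun.

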#### 2.4 Procedure

Treatment is administered by two examiners, each patient receives transcranial electrical stimulation with simultaneous learning of word lists. Each participant of each stimulation type was involved in both learning conditions, meaning that all participants completed both retrieval and restudy learning and testing (experimental procedure in **Figure 1**).

#### (1) Stimulation phase

In the tDCS group, the anode was placed over the left DLPFC (F3), and the cathode was placed over the contralateral supraorbital area (FP2). A direct current of 2mA was applied for 20 minutes during each stimulation session. In the tACS group, the anode was placed in the F3 region of the left dorsolateral prefrontal cortex (DLPFC), and the cathode was placed in the right supraorbital region (Fp2), and the current used was 2 mA AC at 40 Hz, with a stimulation time of 20 min. In the sham group, the stimulation parameters, including the stimulation site and duration, were identical to those of the anodal group. However, during the 10-second ramp-up and ramp-down periods before and after stimulation, patients were unaware that the current was turned off.

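### In a single session with recalls of the full 5 minutes, learning both lists takes about 21 to 37 minutes against 20 minutes of current, so part of the second list is learned off current and the ANOVA has no order term.

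*Protocol*

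**What the plan says.** Section 2.4 (Procedure) states that "each patient receives transcranial electrical stimulation with simultaneous learning of word lists" and that every participant learns both lists. The stimulation paragraph gives tDCS as "A direct current of 2mA was applied for 20 minutes during each stimulation session" and tACS "with a stimulation time of 20 min".

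The learning paragraph sets the task:

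- Each list has 17 words. "Each word was presented for 5 seconds, with a 500-millisecond interval between words".
- The retrieval practice list follows S-T-S-T. In each retrieval, patients are to "write down all the words they had just remembered within 5 minutes".
- "For the restudy list, participants underwent four study sessions (S-S-S": four passes in words, three in notation.
- "Between each learning cycle, participants completed a 3-minute simple arithmetic task". The term *learning cycle* is not defined.
- "The learning of the retrieval practice list and the restudy list was conducted in a randomly balanced manner".

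The immediate test comes once, when all learning is finished. Section 2.2 names three factors (stimulation, strategy, retention interval), and Section 2.5 describes a mixed ANOVA. Neither mentions list order.

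**The concern.** Part of the rationale in Section 1 is that retrieval practice activates the same region that the current is stimulating, so that the two reinforce each other. That requires retrieval to take place while the current is on. If the lists run one after the other and the task outlasts the current, patients who start with restudy (about half, given balanced order) do some of their retrieval practice after it has stopped. The active arms would then mix retrieval with and without current in the stimulation-by-strategy comparison, which is the main question of the trial. With no order term, a weak interaction could not be examined against the timing of the current.

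**Working it through.** **Inputs (Section 2.4).** 17 words per list; 5 s plus 0.5 s per word; two retrievals of up to 5 min; n = 3 or 4 restudy passes; 3 min per break; 20 min of current. The protocol states no total learning time, so there is no figure of its own to reproduce.

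**Assumptions.** One session; current starts with the first study pass; lists run in sequence; recalls last 5 min unless stated otherwise.

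**Formulas.** One study pass = 17 × 5.5 s = 93.5 s = 1.558 min. With g breaks,

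total = (2 + n) × 1.558 + 10 + 3g,

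and the recall length that would just fit = [20 − (2 + n) × 1.558 − 3g] / 2.

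For example, n = 3 and g = 1 give 7.79 + 10 + 3 = 20.79 min; n = 4 and g = 6 give 9.35 + 10 + 18 = 37.35 min.

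**Four placements of the breaks.** A: one break, between the lists (g = 1). B: one break inside each list (g = 2). C: one break between the two S-T pairs and one between all restudy passes (g = n). D: a break between every step within each list (g = n + 2).

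| Reading | n | Total, 5-min recalls | Total without recall | Recall length that fits | Retrieval minutes under current, restudy first | Same, retrieval first | Restudy study time under current if second |
|---|---|---|---|---|---|---|---|
| A | 3 | 20.8 | 10.8 | 4.6 | 92% | 100% | 83% |
| A | 4 | 22.4 | 12.4 | 3.8 | 76.5% | 100% | 62% |
| B | 3 | 23.8 | 13.8 | 3.1 | 62% | 100% | 67% |
| B | 4 | 25.4 | 15.4 | 2.3 | 50% | 100% | 50% |
| C | 3 | 26.8 | 16.8 | 1.6 | 50% | 100% | 33% |
| C | 4 | 31.4 | 21.4 | none | 32% | 100% | 25% |
| D | 3 | 32.8 | 22.8 | none | 48% | 79% | 0% |
| D | 4 | 37.4 | 27.4 | none | 2% | 79% | 0% |

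Restudy learned first is always fully under current. A further break between lists adds 3 min to B, C and D (26.8 to 40.4 min). Counting 16 rather than 17 word intervals changes each total by about 0.05 min. Only a schedule with no break at all would fit with full recalls (17.8 or 19.4 min), and the text does call for breaks.

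**One coverage figure step by step (B, n = 4, restudy first).** Restudy takes 4 × 1.558 + 3 = 9.23 min. Study runs to 10.79, first retrieval to 15.79, break to 18.79, study to 20.35. The second retrieval starts after 20 min, so 5 of 10 retrieval minutes (50%) are under current.

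**Does balance equalise exposure?** Averaging the two orders equally, reading D with n = 3 gives (79 + 48)/2 = 63% of retrieval minutes against (0 + 100)/2 = 50% of restudy time. D with n = 4 gives (79 + 2)/2 = 40% against 50%. B with n = 4 gives 75% for both. Equality is possible but not assured, and even the direction of the difference depends on the reading.

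**Cost of an order factor.** Take the three arms of Section 2.2 with 60 patients split equally (assumed): 20 per arm, about 10 per arm and order. The stimulation-by-strategy test is a test on the retrieval-minus-restudy difference. Error df are 60 − 3 = 57 without order and 60 − 6 = 54 with it; critical F (2 numerator df, 0.05) moves from 3.16 to 3.17. Within one order, the 95% half-width for active versus sham is 2.005 × √(2/10) = 0.90 SD of that difference; for the contrast between orders it is 2.005 × √(4/10) = 1.27 SD.

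**The case against.** - **Recall time is a ceiling.** Five minutes is the most allowed, for a list of 17 words. Patients may stop sooner, and five of the eight readings fit if they do (at 1.6 to 4.6 min per recall). This stands. It does not help the other three, where study and arithmetic alone take 21.4 to 27.4 min.
- **Some readings are less natural.** Reading D puts arithmetic between a study pass and its own test. If a cycle is an S-T pair, D drops out, the maximum is 31.4 min, and only one of the six remaining readings cannot fit. This is fair, but that one (C with four passes) is a natural reading of the text.
- **One session is inferred.** The stimulation paragraph leaves the number of sessions open, and Figure 1, to which Section 2.4 refers for the procedure, is not shown. With one list per session and full recalls, the retrieval list takes 13.1 to 22.1 min and the restudy list 4.7 to 15.2 min; only the retrieval list under D overruns, by 2.1 min. This stands as a condition on the finding. The single immediate test after all learning still points to one block, and no sentence gives each list its own session.
- **An order term is analysis-plan detail.** True: its absence from Sections 2.2 and 2.5 contradicts nothing by itself, and a statistical analysis plan that is not shown may include it. It is recommended here because of the timing problem. That problem and the mismatch between four sessions and S-S-S are in the protocol text.
- **A tempting remedy.** A reader might infer that any claim about concurrent stimulation should rest on patients who did retrieval practice first. That is unsound. In them retrieval is 79% to 100% under current and restudy only 0% to 83%, so a benefit of stimulation equal for both strategies would look like synergy. The sham arm corrects for order without current, not for this unequal exposure.

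**Conclusion.** The concern holds conditionally. Given one session, current starting with the first pass, lists in sequence and full recalls, every one of the eight readings exceeds 20 min, by 0.8 to 17.4 min; five exceed it by 5 min or more. Learning under current is therefore something the stated schedule does not reliably deliver.

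Three stronger readings are not supported. A reader might infer that simultaneous learning definitely fails; the recall ceiling, the unstated number of sessions and the missing figure prevent that conclusion, and at the low end the overrun is trivial. A reader might infer a diluted interaction or lost power; the protocol gives no basis for a size, since any benefit may outlast the current. Nor can one infer that balanced order removes the problem: it spreads the shortfall over both strategies without guaranteeing equal exposure.

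Severity is minor to moderate.

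**What to change.** 1. Section 2.4, opening and stimulation paragraph: state that current starts with the first study pass of the first list and that learning tasks after 20 min are done without current. Limit the claim of simultaneous learning to the tasks inside that window.
2. Section 2.4, learning paragraph: define *learning cycle* so that the place of each break is fixed, and reconcile four study sessions with S-S-S, so that the total time follows from the text.
3. Section 2.5: add list order, already randomly balanced, as a between-subjects factor with its interactions with stimulation and strategy. Keep the stimulation-by-strategy test averaged over both orders as the main test. Report active-versus-sham estimates by order as descriptive only. If an analysis plan already has this term, the wording changes suffice.

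The cost is wording and 3 error df, with no added visits or stimulation. In return, variation due to order leaves the error term of the main test. The drawbacks are that order-specific estimates will be coarse (about ±0.90 SD with 10 per cell) and that the claim about concurrent stimulation becomes narrower.
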